 The guidelines have been developed in conjunction with the upper extremity surgeons to reflect their current practice. The purpose of the guidelines is to reduce inadvertent variability, particularly when residents and other providers provide the post-operative prescription. Despite the guideline, the surgeon is still encouraged to provide the pain medication prescription he/she feels is most appropriate for the patient.

The Patient Education Study Diary includes a daily pain scale, the QoR-15 on day 2, the selected PROMIS short forms on day 3 and knowledge quiz on day 7. It also contains opportunity to report dressing changes, co-analgesic modalities (ice, elevation, etc), and possible medication side effects. There are daily questions regarding confidence, feeling in control, and satisfaction. The final day also has questions regarding how many times the videos were viewed, the number of contacts with a healthcare provider for pain and wound related issues, and concurrent use of other sedating substances (sleeping pills, alcohol, street drugs, other sedating medications). Patients in the control group (wound care) will also record all pain medications used each day along with any side effects of said medications. Participants in the intervention (pain management) group will record their pain medication use in the additional Recovery Medication Diary provided. The patient will return the diary at the first post-operative visit or by mail.

Patients may be contacted by phone within 7-10 days after the appointment if study materials are not complete. Information regarding the initial narcotic prescription, CPT procedure codes, concurrent NSAID prescription, and type of anaesthetic will be obtained from EPIC by chart review.

The patient will be contacted again by phone and/or mail 1 year after surgery (12-14 months) using the contact information available in EPIC to determine the self-reported prevalence of chronic pain and pain medication use (yes or no answers):

1. Do you have pain on a daily or weekly basis?
2. In the past year, have you taken prescription opioid (or narcotic) pain medication most days or most weeks?
3. In the past year, have any other pain medications (prescription or over the counter) most days or most weeks?

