17. **Objectives:** State the research hypothesis or the question that the research will answer. List the research objectives and expected outcomes. **A primary outcome or objective must be identified.** After the statement of the primary objective, secondary objectives may be listed. Objectives should be simple and specific.

Hypothesis: Patient experience and outcome after outpatient upper extremity orthopedic surgery can be improved by a formalized education program (video and handout) regarding post-operative pain management.

Primary outcome:

1. QoR-15 scores (post-operative day "POD" 2),
  - a. 15-question validated outcome measurement tool used in the setting of outpatient surgery which takes about 2.5 minutes to complete and includes pain as one of its outcome domains

Secondary Outcomes:

2. PROMIS short forms administered on POD 3 – (GI belly pain 5a, GI nausea and vomiting 4a, Pain Intensity 3a, Pain Interference 4a, Sleep Disturbance 4a, Cognitive Function 4a)
3. number of narcotic pills used – 7 days,
4. daily pain level (by 0-10 rating scale) – 7 days,
5. patient-reported satisfaction and feeling of control (4 point rating scale)
6. number of pain-related calls/visits to a healthcare provider
7. use of non-narcotic adjunct pain relief medication and modalities
8. incidence of high risk activities (combining narcotics with muscle relaxants/sedatives/alcohol, etc.; combining prn NSAIDs with regularly dosed prescription NSAIDs, exceeding daily recommended doses)
9. incidence of side effects and adverse events,
10. demonstrated patient knowledge as measured by score on the follow-up quiz, and
11. prevalence of chronic opioid use.

Positive improvements in some or all of these measurements are expected with this patient education intervention. The Quality of Recovery-15 survey is a 15-question validated outcome measurement tool used in the setting of outpatient surgery which takes about 2.5 minutes to complete and includes pain as one of its outcome domains

18. **Study Design:** Give a description of the research design including use of placebo, randomization and an explanation of what is experimental. Include type of study: descriptive, retrospective, cross-sectional, longitudinal, prospective observational, pilot, experimental (controlled or non-controlled) or pilot.

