**Outcome Measure Data:**

1. QoR-15 scores (primary outcome),
2. Selected short form PROMIS questionnaires,
3. number of narcotic pills used,
4. daily pain level (by 0-10 rating scale) for days 0-7,
5. patient-reported satisfaction and feeling of control (10 point rating scale),
6. calls/visits to a health care provider for pain or related concerns
7. use of non-narcotic adjunct pain relief medications and modalities,
8. incidence of side effects and adverse events
9. reported frequency of noting pain medication dose times,
10. demonstrated patient knowledge as measured by score on the follow-up quiz, and prevalence of chronic pain, long term narcotic and non-narcotic pain medication use.

Data will be collected by chart review (for demographic data and data pertaining to the surgery, anaesthetic, and initial narcotic prescription), physician and patient reporting, and by patient diary/surveys (which will be completed by the patient at home and returned at the follow-up visit or by mail). Follow-up phone calls will act as a reminder to help encourage completion of the study. Information regarding how many times a video was viewed will be collected by patient questionnaire (measured outcome to be used in analysis), reviewing Mychart data, and counting Youtube hits.

22. **Statistical Analysis:** State how qualitative and/or quantitative data will be analyzed. This must include a statement from a statistician that there is sufficient power to determine the primary study outcome or objective. Other outcomes may be listed as secondary and descriptive. If this is a proof of concept or feasibility study that includes limited efficacy testing, there must be a statistician statement that the appropriate design is in place to determine whether an intervention should be recommended for broader efficacy testing. If a study is meant to be solely descriptive, then results apply only to the sample being studied and conclusions cannot be drawn about the larger population; therefore, the primary outcome or objective must be limited in scope.

Standard descriptive statistics will be undertaken. All data will be integrated into a mixed model ANOVA with appropriate post-hoc comparisons by group as appropriate. Analysis will be carried out with the assistance of a qualified biostatistician.

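### The protocol puts every outcome into one mixed model ANOVA although several secondary outcomes are incidences or yes/no answers, and it gives the satisfaction/control rating two different scales (minor, secondary outcomes only)

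*Protocol*

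**What the plan says.** **Method.** Protocol Section III, item 22 (Statistical Analysis) has a general line on descriptive statistics, then "All data will be integrated into a mixed model ANOVA" with post-hoc group comparisons, and names a biostatistician's help. No other inferential method appears in the protocol.

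**Outcomes.** Item 17 (Objectives) lists among the secondary outcomes "incidence of high risk activities" (item 8), "incidence of side effects and adverse events" (item 9) and the prevalence of chronic opioid use (item 11). Item 15 (Study Abstract) describes the 1-year pain and medication questions as "yes or no answers". It also says that the final diary day asks about "concurrent use of other sedating substances (sleeping pills, alcohol, street drugs, other sedating medications").

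**Rating scale.** Item 17 and item 20 (Methodology, step 7) both give "patient-reported satisfaction and feeling of control (4 point rating scale"). Item 21 (Outcome Measure Data) gives "patient-reported satisfaction and feeling of control (10 point rating scale"). Item 15 says of the diary: "There are daily questions regarding confidence, feeling in control, and satisfaction".

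**The concern.** A mixed model ANOVA assumes roughly normal errors with a common variance. A 0/1 outcome has variance p(1-p), which changes with the rate and shrinks to nothing as events become rare: 0.0475 at p = 0.05 and 0.21 at p = 0.30 (illustrative rates). The outcomes concerned include adverse events and high risk activities, where an interval that is too narrow could suggest that a difference has been excluded when the data cannot exclude it.

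The scale conflict is independent of this. The rating is a named secondary outcome collected daily, and a between-group difference quoted in points means something different on a 4-point and on a 10-point scale.

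**Working it through.** **1. The plan's own figure.** Inputs from Power Calculation and Sample Size: difference 8, SD 25, alpha 0.05, power 0.8 (the text labels it beta). Two-sided n per group = 2 × (1.960 + 0.842)² × 25² / 8² = 153.3, so 154. With 20% attrition, 154 / 0.8 = 192.5, so 193, rounded to 200. The figure reproduces and nothing below changes it.

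**2. ANOVA interval for a yes/no outcome.** With two arms of n patients and observed proportions p1 and p2, the interval is (p1 - p2) ± t × √(s² × 2/n), where s² = [n·p1(1-p1) + n·p2(1-p2)] / (2n - 2) and t has 2n - 2 degrees of freedom. Coverage was found by exact enumeration of the two binomials. All rates are assumed, because the protocol gives none.

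| True rates | n per arm | Coverage | P(no events in either arm) | Coverage given any event |
|---|---|---|---|---|
| 1% vs 0.5% | 154 | 89.0% | 9.8% | 98.7% |
| 2% vs 1% | 154 | 93.5% | 1.0% | 94.4% |
| 3% vs 1% | 154 | 92.7% | 0.2% | 92.9% |
| 5% vs 2% | 154 | 94.9% | 0.0% | 94.9% |
| 10% vs 5% | 154 | 94.9% | 0.0% | 94.9% |
| 30% vs 20% | 154 | 95.0% | 0.0% | 95.0% |
| 1% vs 0.5% | 120 | 82.5% | 16.4% | 98.7% |
| 2% vs 1% | 120 | 89.8% | 2.7% | 92.3% |
| 1% vs 0.5% | 200 | 85.9% | 4.9% | 90.3% |

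The 120 is an assumed number answering at 1 year; 200 is the enrolled number per group.

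At 1% versus 0.5% and 154 per arm, non-coverage is 100 - 89.0 = 11.0 points. The no-event case has probability 0.99^154 × 0.995^154 = 9.8% and never covers the true 0.5-point difference, so it supplies 9.8 of the 11.0 points.

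**3. The sparse cases directly, 154 per arm.**
- 0 vs 0 events: s² = 0, so ANOVA gives 0 to 0. For the Miettinen-Nurminen score interval the limit solves d² = z² × d(1-d)/n × 2n/(2n-1). With k = 3.8415 × 308/307 = 3.854, d = k/(n + k) = 3.854/157.854 = 2.4%, so the interval is -2.4 to +2.4 points.
- 1 vs 0 events: s² = (153/154)/306 = 0.00325, SE = √(0.00325 × 2/154) = 0.65 points, and 0.65 ± 1.968 × 0.65 gives -0.6 to 1.9. The score interval is -1.8 to 3.6.

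**4. Rejection rates.** Under a true null, ANOVA rejects 4.4-5.1% of the time at rates of 2-50%, 3.0% at 1% and 0.7% at 0.5%. The score test gives the same 3.0% and 0.7%. At 3% versus 1% both reject 21.9%; Fisher's exact test rejects 10.3%.

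**5. Daily yes/no data.** Over 7 days, in 8,000 simulated trials with an assumed within-patient correlation of 0.3 or 0.6, linear coverage was 91.4-93.6% at 1% versus 0.5% and 94.9% at 10% versus 5%. The pattern is the same.

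**6. Rating scale.** Items 17 and 20 agree on 4 points; item 21 says 10. If the scales run 1-4 and 1-10 (end points assumed; none are stated), one point is 1/3 = 33% of the range on one and 1/9 = 11% on the other.

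**The case against.** The strongest reply is that a linear model on a 0/1 outcome in two randomised arms estimates a risk difference, and does so well at ordinary rates. That stands, and it limits the point to sparse outcomes. A reader might infer from the 89.0% that the ANOVA interval is generally too narrow for rare events. The table does not support that: most of the shortfall is the no-event case, in which a careful analyst would see that ANOVA supports no inference. Real undercoverage remains at some other rates, but at 3% versus 1% and 154 per arm the unstratified score interval itself covers only 93.6%, less than a point better than 92.7%.

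Nor do the documents show that these outcomes are rare. Street drug use is one diary component, not an outcome. High risk activities is a composite that includes alcohol and sedatives, which the Background says some patients use regularly, and side effects are pooled with adverse events. Rarity is plausible only for individual components.

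Item 22 is also a short answer on an ethics application. The form allows other outcomes to be listed as secondary and descriptive, and a separate analysis plan may assign methods by outcome type. This lowers the severity, but the sentence as written exempts nothing, and the descriptive line is tied to no outcome.

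On the scale, a reader might infer that no repeated-measures model can be chosen, or that no result could be interpreted. Neither follows: a linear or ordinal mixed model can serve either scale, and the diary as administered will presumably carry one format that a report would state. The contradiction between the three places still stands.

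**Conclusion.** Both parts hold, as minor points confined to secondary outcomes.

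The stated method does not suit the incidence and yes/no outcomes when events are sparse. It gives a degenerate interval with no events, a narrow one with a single event, and modest undercoverage at some low rates. Which outcomes, if any, fall in that range rests on assumed rates. From about 5% versus 2% upward there is no material harm. A reader might also infer inflated false-positive findings; none was found, and the low rejection at 1% and below reflects sparse data, since the score test behaves identically there.

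The scale conflict needs no assumed rates. It is a plain contradiction about a named secondary outcome, and it affects what a difference in points means.

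**What to change.** **Item 22.** Limit the mixed model to QoR-15, PROMIS, daily pain and quiz scores. For yes/no outcomes, state a risk difference with a score (Miettinen-Nurminen) interval, or logistic regression. Any-versus-none coding, stratification by the six prescription classes, penalisation for rare events and a count model for pills are options, not corrections. Any-versus-none coding discards frequency where events are recorded daily. Fisher's exact test should not be the default, because it loses power.

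**Items 17, 20 and 21.** Reconcile the 4-point and 10-point descriptions with the diary as administered, before the data are analysed, and state the end points.

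**Cost.** Wording, one decision on the scale and a little more analysis work. The sample size does not change, and at 3% versus 1% the score method rejects as often as ANOVA (21.9%).

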**Power Calculation and Sample Size:**

The QoR-15 score is a validated outcome metric for quality of recovery (Stark 2013) and is the primary outcome measure for this study. Thus, the QoR was chosen for the power analysis and sample size calculation. Using data from Stark et al 2013, the expected values for the QoR score are average ( $\mu$ ) of 120 and standard deviation ( $\sigma$ ) of 25. We would consider a difference of 8 points to be

clinically significant. Thus, using these values and with an  $\alpha$  of 0.05 and  $\beta$  of 0.8, the calculated sample size is  $n = 154$ . Our study design will allow for a maximum attrition of up to 20% (39 patients), thus we will enroll 200 patients per group (rounding up from 193).

Our group performs approximately 2000 procedures annually (1,973 in FY2016), of which we anticipate 80% will be eligible for this study. Assuming a 50% enrollment rate, it is reasonable to project completion of enrollment in 6 months. Notably, the enrollment rate amongst eligible patients for our completed study on narcotic use after minor hand surgery was greater than 95%. However, this study does require more patient engagement, and so a more conservative estimate has been used. The video length as well as the length and complexity of the diary and surveys are being minimized. Patients will be contacted by phone (with permission) as well as have contact at their follow-up appointment(s) to assist with completion and return of materials. Self-addressed stamped return envelopes will be provided when the patient fails to bring study materials to the first post-operative visit.

Statistical review was conducted by: [name] (name of statistician)  
Carilion (Department/Institution of statistician)

If no statistical review was done, explain why:

#### **SECTION IV: RISKS AND BENEFITS**

23. Summarize the possible risks to subjects and how they have been minimized in the study design. Include risk of psychosocial harm (e.g., emotional distress, embarrassment, breach of confidentiality), economic harm (e.g., loss of employment or insurability, loss of professional standing or reputation, loss of standing within the community) and legal jeopardy (e.g., disclosure of illegal activity or negligence), as well as known side effects of study medication, if applicable, and risk of pain and physical injury. Define the level of risk (minimal risk, risk but with potential benefit to patient, risk but no benefit to patient). Describe any procedures that will be used to prevent or minimize risks or discomforts. Note: Most studies create at least a small risk of breach of confidentiality or privacy.

This is a minimal risk study. Risks include breach of confidentiality due to the collection of patient protected health information. All collected data will be disclosed in the consent form.

24. Describe all costs, if any, subjects may incur as a result of being in this study.

Subjects will not incur any costs additional to those they would incur as part of their routine care.

25. Describe how subjects will be compensated for injury incurred as a result of being in the study.

This is a minimal risk study. Subjects will not be compensated for injury incurred as a result of being in this study.

26. Is any deception used in the study or any aspect of the study kept secret from the subjects, such as the full purpose of the study?

Yes  No

• If yes, describe the deception involved and the debriefing procedures:

27. Describe any direct benefit to individual subjects, to the group of individuals with the disease process you are researching, and/or to society based on scientific knowledge gained. Explain how the potential benefits offered by this research outweigh the risks. (Please note: payments, gifts, or other free services given as a token for participation are not benefits, but instead are classified as compensation.)

The investigators believe that both the Pain Management and Wound Care educational programs help patients be more prepared for their surgical recovery, although this has not been demonstrated experimentally. Data gathered during this study may help researchers understand what educational materials are helpful to patients making pain management decisions, and how these materials influence their pain management choices after surgery.

## SECTION V: RECRUITMENT

28. Number of Subjects/Enrollment Goal. The enrollment goal must match the number of subjects needed to meet the primary outcome. If this is a retrospective record review, this figure is the number of records that will be used for analysis. Note: Once research begins and it is anticipated the enrollment goal will be exceeded, the IRB must be notified. In some cases, prior IRB approval must be given to exceed the enrollment goal.

Locally: 400 At all Sites:

**\*\*\*If this study is a retrospective record review only, you may skip to Section VII\*\*\***

Carilion IRB Application  
(July 2016)

- 4 -

29. Will subjects receive any compensation or gifts to participate?

Yes  No  N/A

- If yes, specify payment amount, how it will be prorated and how payment will be made: The patient will be provided a "thank you" gift in the form of a Carilion branded "I made a DIFFERENCE!" cup (see recruitment flyer for image). The cups have been approved by Carilion Marketing. They are valued at \$3.87. The cup will be given to the patient at their first post-operative visit, regardless of whether the patient has completed the study, withdrawn from the study, or is yet to return study materials.

30. Will you, the sponsor, or Contract Research Organization offer any fee to physicians for the referral of potential subjects?

Yes  No

31. Will recruitment materials be used?

Yes  No

If yes, check all that apply and include with this submission:

 Brochure	 Radio/Television script
 E-mail	 Newspaper Ad
 Recruitment letter	 Website advertisement (including Facebook, Craigslist, etc.)
 Flyer/Poster	 Telephone or in-person script
 Clinical trial website posting	 Other (please specify):

### STEP 1: IDENTIFICATION OF POTENTIAL SUBJECTS

To "identify" a potential subject refers to steps you plan to take to determine which individuals may qualify to participate in your study so that you can decide which individuals to contact about taking part.

32. How do you plan to identify potential subjects? (check all that apply)

- Medical Chart Review, Clinic Schedule Review, or QA-QI Database Review (own patient population)  
*\*Study team requests Waiver of Informed Consent and, if any HIPAA identifiers are collected, a Waiver of HIPPA Authorization for recruitment purposes*
- Medical Chart Review, Clinic Schedule Review, or QA-QI Database Review (other physicians/practices patient population)  
*\*Study team requests Waiver of Informed Consent/HIPAA Authorization for recruitment purposes*
- Potential subjects will not be directly identified by the researchers. The potential subject will obtain IRB-approved written information about the study from his or her health care provider/faculty or from an advertisement, flyer, brochure, website, etc. The potential subject would then contact the researcher if he or she is interested.
- Researchers who ARE NOT treating clinicians of potential subjects will ask treating clinicians for referrals of eligible patients interested in the study. Treating clinicians identify potentially eligible patients and provide researchers with patient contact information with patient permission documented (e.g. email/letter to researcher from treating clinician states patient permission given. Researcher documents permission in research record.)  
*\*Study team requests Waiver of Informed Consent/HIPAA Authorization for recruitment purposes*
- Contact information will be provided by a patient's Carilion health care provider without the patient's knowledge to the researchers AND this is a minimal risk study that does not involve investigative drugs, devices, biologics or medical or surgical procedures.  
*\*Study team requests Waiver of Informed Consent /HIPAA Authorization for recruitment purposes*

- Review of Registry/Database in which individuals have previously signed a consent giving their permission to be contacted for future studies
- Student Records
  - \**Study team requests Waiver of Informed Consent for recruitment purposes*
- Other – please explain: see 33

33. Please describe the identification process. List all information you plan to collect during the identification process prior to contacting potential subjects. This includes the inclusion/exclusion criteria and demographics to determine if a person qualifies for a study before contacting that person to be a potential subject.

Treating providers, who are also investigators, will identify potential subjects that are 18 years of age or older and are planning/scheduling outpatient orthopedic surgery and will ask the patient (personally or through a treatment team delegate) if they would mind meeting with the designated enrollment investigator present in the clinic that day.

Script:

"Mr/Ms \_\_\_\_\_. I think you would qualify to participate in a study about educating patients before surgery. The study involves watching a video designed to help you prepare for surgery. Would you be interested in meeting with a study representative to see if you qualify and learn more? Don't feel any pressure - it won't affect your care either way."

If a patient does not wish to meet with the designated enrollment investigator, the designated enrollment investigator will be informed that one patient declined to meet with them, and that information will be retained for tracking purposes. If the treating provider knows that a patient who is meets inclusion criteria would not qualify for the study due to exclusion criteria, he or she will also pass on the information that one patient who is planning surgery was not referred for consideration for failing to meet exclusion criteria, and this information will be recorded.

34. Who will conduct the identification process?

- Principal investigator
- Other investigator (specify): [name], [name], [name], [name], [name], [name]
- Research coordinator (specify):
- Other research team member (specify):

Carilion IRB Application  
(July 2016)

- 5 -

